
During the iKanEat protocol, we expect the child to lose weight during weeks 10-14 as the children taper off the tube. We inform parents of this expected weight loss and monitor the children closely. Despite this, in the previous trial there were instances of parents withdrawing their children during this weight loss period despite the physician guidance that the weight loss was expected and safe. It is critical that we learn more about this stressful period of the iKanEat protocol so we can better help parents through this transition. The current study design will allow us to learn more about how and when parent stress changes throughout the protocol in order to target supplemental treatment efforts related to parent stress.

Quality of Life.

Our most recent study (HD066629) also examined the role of pain and quality of life in tube weaning. Findings demonstrate improvement in pain symptoms ($t = 1.85$, $p = .006$) and in several areas of quality of life (i.e., growth and development, $t = -2.285$, $p < .05$; behavior, $t = -2.376$, $p < .05$; general health perceptions, $t = -2.232$, $p < .05$; parental impact: emotional and time, $t = -3.718$, $p < .005$) in the transition from tube to oral feeding.(11) In the current protocol we will assess whether successful transition to oral feeding has an effect on parent and child quality of life.

Remote Interventions.

CONFIDENTIAL

This material is strictly confidential and is intended solely for the guidance of clinical investigation. Do not disclose or use except as authorized in writing by the study sponsor

Our team has extensive experience delivering multidisciplinary feeding team clinical visits via interactive televideo. These visits are delivered as part of routine feeding team care in our clinic, and include both new patient visits and return patient visits. This clinical experience will serve our team well regarding the current scope of work.

Gut Microbiota

The gut microbiota refers to the species of bacteria living in the gut, and plays an essential role in digestive and immune function. Little is known about the effect formula feeding has on the microbiome, and the effects of transitioning from tube feeds to oral feeding. In the current protocol, we will assess whether successful transition to oral feeding has an effect on the gut microbiota.

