3.2 Primary Study Endpoints

Percent Kilocalories Obtained Orally will be the primary study endpoint. This measure will be obtained using the three day 24 hour food recall. The 24hr food recall is a standardized five-pass method, developed by the US Department of Agriculture for use in national dietary surveillance. Although there are weaknesses to every method of dietary assessment, this one was selected as it is widely used in several large trials and data suggest it is the most valid and reliable method of dietary assessment for children (35) The data will be collected using highly standardized probes by trained research staff, and parents will be presented with paper food models and measuring devices prior to interviews to reference during the recall. Recalls will be analyzed with the Nutritional Data System for Research, version 2016; University of Minnesota, Minneapolis, MN. Although a plethora of information is available from this analysis, the current study will focus on total daily oral calorie intake. This measure will be completed the week following Clinic Visits at weeks 0, 10, 14 and 24.

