3.3 Secondary Study Endpoints

Parent stress and parent and child quality of life will be the secondary study endpoints and be completed by parents at Clinic Visits at weeks 0, 10, 14, and 24.

1. Parent Stress (The Pediatric Inventory for Parents – PIP36). Parent stress will be measured via the Pediatric Inventory for Parents, a 52 item parent questionnaire developed to measure parent stress around caring for a medically complicated child. The measure has a total and four domain scale scores (communication, medical care, role function, emotional function). For the purposes of the current study, we will use only the total score. The measure has been shown to be a valid and reliable measure of pediatric illness-related parenting stress (36).
2. Child Health-Related Quality of Life (Infant Toddler Quality of Life – ITQOL47). Child quality of life in children <5 years old will be measured with the Infant Toddler Quality of Life short form questionnaire, validated for children 2 months through 5 years of age. The ITQOL has 47 items which result in 9 multi-item scales with well-established reliability (Cronbach's alpha > .70) and validity. Similar to our previous work (11), we will use the multi-item scales in our analyses.
3. Child Health-Related Quality of Life (Child Health Questionnaire Parent Form – CHQ-PF50). Child quality of life in children \geq 5 years old will be measured with Child Health Questionnaire Parent Form questionnaire. The parent-reported CHQ is normed for ages 5-to-18 and measures 14 unique physical and psychosocial concepts. The CHQ has 50 items and scores for the parent-reported versions can be analyzed at the concept level (CHQ Profile Scores) or combined to derive an overall physical and psychosocial score, (CHQ Summary Scores).
4. Parent Quality of Life (SF-36v2). Parent Quality of Life will be measured with the widely used Parent Quality of Life Short Form 36, version 2. Over 4000 studies have used the SF-36, making it a widely accepted measure, and v2 has improved reliability ($\alpha = .73-.90$), and validity (38). The 36 questions with 5 point scales have 8 scaled scores: vitality, physical functioning, bodily pain, general health perceptions, physical role functioning, emotional role functioning, social role

CONFIDENTIAL

This material is strictly confidential and is intended solely for the guidance of clinical investigation. Do not disclose or use except as authorized in writing by the study sponsor

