To address Aim 1, analyses will be conducted using Generalized Linear Mixed Models with a logit link within SAS Proc GLIMMIX to model the binary outcome of transitioned to oral feeding (y/n) defined as at least 90 percent of calories consumed orally. Fixed effects (dummy variables) will be entered for each site as described by McNeish and Stapleton (2016) to account for the clustering of the participants within sites. This will result in essentially, a logistic regression model with appropriate standard errors. Sex, age at initiation, treatment condition, and interactions with treatment condition will enable us to examine the effect of group assignment on successful transition to oral feeding by week 24. Interactions between treatment group and sex will be examined but will not be sufficiently powered to reach definitive conclusions about sex differences. In addition to overall effects, subgroup analyses will be reported for males and females to examine treatment effects within sex groups.

To address Aim 2, we will determine whether any of our participants in either group have adrenal sufficiency levels outside of the normal range at any time point. Should any participant have levels outside of the normal range, we will descriptively examine the individual characteristics associated with this, including group assignment, medical diagnoses, sex, and age at initiation. These characteristics will be reported descriptively.

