To address Aim 3, we will model parent stress levels, child quality of life, and parent quality of life for participants in both treatment conditions over the four measurement occasions using General Linear Mixed Models. As in Aim 1, fixed effects for site will be added to the model as will sex and age at initiation. Once the shape of the trajectory over time has been modeled, a successful transition to oral feeding indicator, defined as consuming 90% or more of calories orally, will be added to the model at level 2. For 3A, the primary variable of interest will be the time by successful transition interaction on parental stress level. Estimate statements will examine group differences in stress at week 14 and 24. To address hypothesis 3B regarding Quality of Life outcomes, we will initially model the trajectory over time for each outcome with the same set of predictors as in 3A. Of primary interest will be the time by successful transition interaction on subscales for parental quality of life and the parent impact time, general health perceptions, growth and development, and parent impact emotional subscales for child quality of life which showed the greatest response to intervention in our pilot data. It is expected that some subscales such as general health perceptions and parent impact time will show more response to intervention than others. A significant positive slope for some quality of life indicators are hypothesized for those children who transition to oral feeding while stable or declining quality of life ratings are expected for those who are unable to transition to oral feeding. Finally, to complete our analyses of sex as a biological variable (SABV) we will assess study outcomes by gender.

To address Aim 4, the Shannon Index⁶⁰ will be used to determine microbial diversity. Data analysis will be completed using the paired t-test unless the data is not normally distributed in which case analysis will be completed with the Wilcoxon Signed Rank test to compare the index values of patients on each diet.

Heterogeneity of Subjects

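### Aim 3's success-group comparison cannot tell an effect of transition on parent stress from an effect of parent stress on transition

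*Combined protocol and SAP*

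**What the plan says.** Section 2 frames Aim 3 as the effect of moving from tube to oral feeding on parent stress and quality of life. Hypothesis 3A predicts a temporary rise in stress at week 14 and a return to baseline by week 24.

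Under Planned Analyses in section 7.1, stress is modelled "over the four measurement occasions using General Linear Mixed Models". Site, sex and age at initiation are the named covariates. Once the trajectory is fitted, a success indicator "defined as consuming 90% or more of calories orally, will be added to the model at level 2" enters, so each child carries a single fixed value. For 3A, "the primary variable of interest will be the time by successful transition interaction on parental stress level", and "Estimate statements will examine group differences in stress at week 14 and 24".

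The Aim 3 text does not say at which week success is judged. The only dated definition is in Aim 1: "to examine the effect of group assignment on successful transition to oral feeding by week 24".

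On timing, section 3.3 has the stress form "be completed by parents at Clinic Visits at weeks 0, 10, 14, and 24". For the diet recall that determines success, section 3.2 says: "This measure will be completed the week following Clinic Visits at weeks 0, 10, 14 and 24".

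Section 1.3 (Parent Stress) reports that "in the previous trial there were instances of parents withdrawing their children during this weight loss period", although physicians had advised that the loss was expected and safe.

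The Aim 3 analysis has no adjustment for earlier stress, no time-by-arm term, and no caution about the direction of the association.

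**The concern.** An indicator settled late in the study is used to explain stress recorded earlier. If more stressed families are more likely to abandon the wean, children who fail will have had more stressed parents, even if transition has no effect on stress. The planned term and contrasts would then show a difference between success groups, and Aim 3 would read it as a consequence of transition.

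The direction matters. The artefact puts successful families below unsuccessful ones at week 14, whereas Hypothesis 3A predicts that transition raises stress then. It could therefore hide a real rise, or suggest that transition relieves stress. Section 1.3 says the findings on parent stress will be used to target supplemental treatment efforts.

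**Working it through.** The plan gives no figure for this bias. Its Aim 3 figures are detectable effect sizes. For 60% success and N=60 the plan states d=.59. The two-sample formula at two-sided .05 and 80% power gives (1.96 + 0.84) x sqrt(1/36 + 1/24) = 2.80 x 0.2635 = .74. That mismatch is a separate matter, and nothing below depends on it.

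**Step 1: order of measurement.** If success is judged at week 24, stress at weeks 0, 10 and 14 precedes it. If it is judged at week 14, weeks 0 and 10 precede it. So does the week-14 form, because it is completed at the visit and the recalls follow over the next week (sections 3.2, 3.3 and 6.8).

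**Step 2: what the week-14 contrast compares.** Section 6.4 starts the taper five days after the week-10 visit at 10% a day, so tube feeding ends about 5 + 10 = 15 days after that visit. Section 6.8 has tube feeding stopped by week 14 for everyone. By protocol, later successes and later failures are both off the tube at week 14, so the contrast does not isolate tube cessation.

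**Step 3: size under assumed links.** From the plan: four visits, N=60 (and 72), 60% success. Assumed, because the documents are silent: total SD of stress 1, within-person correlation .3, .5 or .7, two-sided alpha .05, and an odds ratio (OR) of failure of 1.5 or 2 per SD of the driver. Transition has no effect on stress in any run. The time-by-success test has 3 df with unstructured covariance. There were 4,000 simulated trials per setting, and 2,000 for the week 0-14 rise.

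Rejection rates at N=60 (ranges are over the three correlations):

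| Driver of failure | OR per SD | Time by success | Week-14 contrast |
|---|---|---|---|
| None | 1 | about 5% | about 5% |
| Week-14 stress level | 1.5 | 8-11% | about 30% |
| Week-14 stress level | 2 | 13-26% | about 68% |
| Week 0-14 rise | 1.5 | 20-21% | not tabulated |
| Week 0-14 rise | 2 | 50-53% | not tabulated |
| Stable stress proneness | 1.5 | near 5% | 13-22% |
| Stable stress proneness | 2 | near 5% | 26-52% |

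At N=72, correlation .5 and week-14 level as driver, the interaction rejects in 11% (OR 1.5) and 22% (OR 2).

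**Step 4: hand check of the week-14 row.** If stress is roughly normal within each group, the group difference is d = ln(OR) x (1 - 0.6 x 0.4 x d^2).
- OR 1.5: 0.405 x (1 - 0.24 x 0.152) = 0.39.
- OR 2: 0.693 x (1 - 0.24 x 0.397) = 0.63.

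The simulated week-14 differences are -0.39 and -0.63 SD, with successes lower. The standard error is 0.2635 x sqrt(1 - 0.24 x d^2), or 0.259 and 0.251. The ratios are 1.51 and 2.51, so approximate rejection rates are Phi(1.51 - 1.96) = 33% and Phi(2.51 - 1.96) = 71%. These are close to the simulated 30% and 68%.

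**Step 5: alternatives on the same kind of null data.**
- Time by randomized arm: 4.4-5.9% in every setting.
- Week-24 stress on prior transition status, adjusted for stress at weeks 0, 10 and 14: 4.4-5.7% when measured week-10 or week-14 stress drives failure. Under stable proneness it is 5.6-8.9% at OR 1.5-2, and up to 14.7% at OR 3.
- Same-visit oral status with within-child contrasts plus lagged stress: 11-33% when measured stress drives failure.

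**The case against.** The strongest objection is that section 1.3 does not establish the mechanism. A reader might infer that the documents say stress makes parents withdraw and that a withdrawn child counts as a failure. They say neither. Section 1.3 reports instances of withdrawal during expected weight loss and calls the period stressful. Section 4.4.2 still seeks diet recalls after withdrawal, so a withdrawn child can be classified on data. The path from stress to failure is plausible, not documented.

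Second, section 7 makes the protocol-compliant population primary. Many families who give up may be excluded from it, which would replace part of this bias with selection. The secondary all-treated analysis would keep them if they are assessed. This stands as a limit on the size, but it does not make the comparison causal.

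Third, a reader might size the problem from a t-test of the week 0-14 change between success groups. When that same change drives failure, such a test rejects in 31-37% (OR 1.5) or 68-75% (OR 2) of null trials at N=60 to 72. The plan does not specify that test, and its interaction test rejects less often.

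Fourth, dating the Aim 3 indicator at week 24 is an inference from Aim 1. That is correct, but Step 1 shows a week-14 date does not remove the problem.

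**Conclusion.** The concern holds as a limit on interpretation. The time-by-success term and the week 14 and 24 contrasts are associations, and the plan treats them as the effect of transition.

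The size is illustrative only. It rests on an assumed OR of 1.5-2 per SD and correlations of .3-.7, none of which the documents supply; with no link there is no bias. Under those assumptions, at N=60 and 60% success, the interaction rejects in about 8-26% of null trials (week-14 level) or 20-53% (week 0-14 rise). The week-14 contrast rejects in about 30-68% when week-14 level drives failure. If only stable proneness matters, the interaction is unaffected, but the week-14 contrast is still inflated (13-52%).

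A reader might infer that the artefact would falsely confirm Hypothesis 3A, or that treatment efforts would certainly be misdirected. The first has the sign wrong, since the artefact runs against the predicted week-14 rise. The second goes beyond anything the documents show.

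**What to change.** Change the Aim 3 wording in section 7.1 before analysis:

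1. State the week at which success is judged for Aim 3. Report the success-group trajectories and the week 14 and 24 contrasts as descriptive associations, not as the effect of transition.
2. Add the time-by-randomized-arm comparison of stress in all randomized children with data. Note that it answers a different question: the effect of assignment to megestrol on parent stress.
3. For an effect of transition, model week-24 stress on oral-feeding status from the week-14 recall, adjusting for stress at weeks 0, 10 and 14, and label it observational. The week-14 recall follows the first three stress forms and precedes the last, so the time order is right.

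Do not use same-visit status with within-child contrasts plus lagged stress. Each recall follows that visit's stress form, so the bias remains (Step 5).

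The data are already collected, so the cost is wording and one extra model. The price is a weaker causal claim for Aim 3. Item 3 reduces the bias but does not fully remove it if stable stress proneness drives failure. It will also be imprecise if few children are below 90% oral at week 14, a count the documents do not give.

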1.3 Review of Literature

Feeding

Our team has published several studies of pediatric feeding difficulties. Our early work examined the relationship between feeding difficulties and medical complexity (27), and found that by the time of introduction of solid food, preterm children more often demonstrated difficulty than full-term children. Also, medical factors, primarily the need for breathing assistance, accounted for more of the variance in this relationship than prematurity alone. We have also assessed parent perceptions of mealtime behaviors in children who are tube fed, and learned that parents report surprisingly high levels of stress around the mealtime, both for themselves and their children (28). We have also examined pediatric sensory processing issues related to feeding problems (29) and found that 67% of children who present for treatment have sensory profile scores in the abnormal range. Also, co-occurring diagnoses are frequent in the areas of developmental, gastrointestinal, and neurological areas. This foundational work led to the multidisciplinary protocol which we call iKanEat that was designed to move these complicated children to oral eating on an outpatient basis.

Clinical Data: iKanEat

In 2008, our team published a retrospective chart review of the first 9 patients to undergo our iKanEat tube weaning protocol clinically (30). At that time, the protocol included two medications (amitriptyline and megestrol) as well as behavioral and oral motor/sensory components. Results from this initial retrospective study indicated that the nine initial patients were 100% orally fed at the end of the intervention period, and 8 of the 9 were 100% orally fed six months later (one patient with cerebral palsy had stamina issues and was only able to sustain 50% of intake orally over the long term). This pilot work led us to NIH funding to conduct a randomized controlled trial of amitriptyline, one of the two medications in the protocol (HD066629). The findings (11) suggest that 100% of children who completed the protocol moved from tube feeding to total oral feeding, regardless of group assignment (amitriptyline, placebo). More specifically, of the children who completed the 6 month protocol, % kilocalories/day obtained orally (our primary outcome measure) increased statistically significantly from $M = 31.51\%$ ($SD = 16.09\%$) to 100%. Therefore, it does not appear that amitriptyline is a necessary component of the iKanEat protocol.

Parent Stress

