Aim 3: To examine the effect of the transition from tube to oral feeding on parent stress and parent and child quality of life. Hypothesis 3A: The transition to oral feeding will temporarily increase parent stress at week 14 at the cessation of tube feeding, with a return to baseline by week 24. Hypothesis 3B: The transition to oral feeding will increase parent/child quality of life at 24 weeks compared to week 0. Children with feeding tubes have few options for treatment other than extensive inpatient stays and expensive day treatment programs. iKanEat offers an outpatient, less intensive, empirically supported effective treatment option that can improve the lives of children and families. It is imperative that we determine the efficacy and safety of the protocol including 4 weeks of megestrol before we move toward broad dissemination of the iKanEat protocol.

Aim 4: To examine the effect of the transition from tube to oral feeding on the gut microbiome. Hypothesis 4A: The transition to oral feeding will increase the variety of food consumed orally, thus diversifying the gut microbiome by week 24. Hypothesis 4B: Children who are on a blended diet formula at week 0 will have a more diverse microbiome than children on commercially prepared formula prior to transitioning to oral feeding (Week 0, 10). Little is known about the gut microbiota of children who transition from formula feeding to oral feeding. Determining the changes in the gut microbiome could add to general knowledge about how the gut microbiome adapts to changes in diet over time in children who transition from commercial or blended formulas to a diet consumed orally.

CONFIDENTIAL

This material is strictly confidential and is intended solely for the guidance of clinical investigation. Do not disclose or use except as authorized in writing by the study sponsor

3 Study Design

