6.8 Clinic Visit 3 (Week 14)

Participants will return to clinic to complete vital signs and blood draw (morning cortisol). The morning cortisol lab value must be taken at least 5 days after the final dose of study drug, so verify with the family when the last dose will be taken before scheduling the Week 14 visit. If an abnormal morning cortisol value is measured, follow the redraw procedures under section 3.4 Primary Safety Endpoints. Height and weight will both be taken in triplicate via calibrated equipment by a trained staff member. At the visit they will also complete the PIP, ITQOL or CHQ, RAND SF-36, PedsQL and schedule three 24 hr Dietary recall phone calls over the coming week. Participants will bring in a frozen stool sample. Tube feedings and megestrol will have ceased. Parents will be asked about any major changes in their health, appetite, and medications

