7.1 Sample Size Determination and Statistical Methods

For Aim1 (To assess the efficacy of megestrol as part of the 24 week iKanEat protocol), if at least 90% of the treatment group successfully transitions (in pilot 100% successfully transitioned), with 72 participants, we would have .80 power to detect an odds ratio of .21. With 60 participants, we would have power to detect an odds ratio of .18. If only 75% of the treatment group successfully transitions, we will still have .80 power to detect an odds ratio of .25 with our smallest expected sample size of 60.

For Aim 2 (To assess the safety of megestrol as part of the 24 week iKanEat protocol), all analyses are descriptive, so a power analysis is not conducted.

For Aim 3 (To examine the effect of the transition from tube to oral feeding on parent stress and parent and child quality of life), with 60 participants, we would have .78 power to detect differences in slopes over the four data points equivalent to a standardized effect size of $d=.75$ or larger. With a sample size of 72, there will be .80 power to detect a difference in slopes equivalent to a standardized effect size of .70. To answer those questions in which the grouping factor is success in treatment, such as 3A (The transition to oral feeding will temporarily increase parent stress at week 14 at the cessation of tube feeding, with a return to baseline by week 24) and 3B (The transition to oral feeding will increase parent/child quality of life at 24 weeks compared to week 0), assuming that 60% of the participants across groups are successful, we would have sufficient power to detect effects equivalent to a standardized effect size of $d=.42$ or larger. With a sample size of 60, the minimum detectable effect size would increase to $d=.59$. If 70% percent are successful, with 72 participants we can detect effects equivalent to $d=.61$, and with 60 participants $d=.70$. These are moderate sized effects.

Planned Analyses

CONFIDENTIAL

This material is strictly confidential and is intended solely for the guidance of clinical investigation. Do not disclose or use except as authorized in writing by the study sponsor

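### The named test for Hypothesis 3A compares successful with unsuccessful families, so it does not test the within-family stress change that the hypothesis states; for 3B the gap is smaller, and the test weakens as success rises.

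*Combined protocol and SAP*

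**What the plan says.** Section 2 (Aim 3) states both hypotheses as changes over time and mentions no comparison with children who fail. Hypothesis 3A, on parent stress, reads "The transition to oral feeding will temporarily increase parent stress at week 14 at the cessation of tube feeding, with a return to baseline by", and the sentence closes by naming the final visit, at 24 weeks. For 3B: "The transition to oral feeding will increase parent/child quality of life at 24 weeks compared to week 0".

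The Planned Analyses text in section 7.1 fits a mixed model over the four visits. It models the shape of the trajectory first, then adds an indicator of success (90% or more of calories by mouth). The designated terms come from that second step. For stress: "For 3A, the primary variable of interest will be the time by successful transition interaction on parental stress level". For quality of life: "Of primary interest will be the time by successful transition interaction on subscales for parental quality of life". The only Estimate statements named for stress are group differences at weeks 14 and 24. For 3B the text also predicts rising ratings in children who transition and flat or falling ratings in those who do not.

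The Aim 3 sample-size text treats success as the grouping factor, "assuming that 60% of the participants across groups are successful" in one case and 70% in the other. Section 1.3 reports that in the previous trial "100% of children who completed the protocol moved from tube feeding to total oral feeding", in both arms.

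**The concern.** The null of the interaction is that families of successful and unsuccessful children follow the same path. The null of 3A is that stress does not change when tube feeding stops. Section 6.4 starts the same taper in every child after the week 10 visit, and by week 14 the plan expects that "Tube feedings and megestrol will have ceased". Section 1.3 (Parent Stress) ties the stressful period to weight loss during that taper. A rise common to all families is therefore a plausible form of 3A, and it is the form the named test cannot detect.

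The reverse can also happen. If only families of unsuccessful children change, the interaction is non-zero although families who made the transition did not change.

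The interaction also depends on having enough unsuccessful children. The better the programme works, the less this test can show.

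**Working it through.** **1. The plan's own detectable effects.** Section 7.1 gives d = .42 (72 families, 60% success), .59 (60, 60%), .61 (72, 70%) and .70 (60, 70%). It does not state alpha, the exact power or the within-family correlation for these. I assume alpha .05 and power .80, and use a two-sample t test with noncentrality d × √(n1·n2/(n1+n2)) on N − 2 degrees of freedom.

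| N, success | Plan | Two-sided | One-sided | Two-sided power at plan's d |
|---|---|---|---|---|
| 72, 60% | .42 | .68 | .60 | 41% |
| 60, 60% | .59 | .75 | .66 | 60% |
| 72, 70% | .61 | .73 | .65 | 65% |
| 60, 70% | .70 | .80 | .71 | 69% |

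Only the last figure is close, and only one-sided. The four also disagree with each other. Moving from 60% to 70% success should multiply d by √(.24/.21) = 1.07; the plan's ratios are .61/.42 = 1.45 and .70/.59 = 1.19. Moving from 72 to 60 families should multiply d by √(72/60) = 1.10; the plan's ratios are .59/.42 = 1.40 and .70/.61 = 1.15. A gain from repeated measures cannot explain this, because no single variance factor fits all four.

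**2. A shared rise.** If both groups change by the same amount, the expected group difference in change is zero, so the interaction rejects with probability alpha whatever the success rate. A simulation with 60 or 72 families, correlation .5 (assumed) and a .59-SD rise in everyone gave about 5% for the interaction. The within-family contrast over all families gave about 99%.

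**3. A rise in successful families only.** Assume 60 families and a 0.5-SD rise from week 0 to week 14. The SD of the change is √(2(1 − ρ)), which is 1.00 visit SD at ρ = .5. At ρ = .5:

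| Success | Groups | Interaction power | Within-family power, successes |
|---|---|---|---|
| 60% | 36/24 | 46% | 83% |
| 70% | 42/18 | 41% | 89% |
| 76% | 46/14 | 36% | 91% |
| 90% | 54/6 | 21% | 95% |

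The correlation matters a good deal. At 60%, 70% and 76% success, interaction power is 35%, 31% and 28% at ρ = .3, and 84%, 79% and 72% at ρ = .8. At 76% success, the within-family contrast has 80% power at ρ = .3 and nearly 100% at ρ = .8. If instead only unsuccessful families rise by 0.5 SD, the interaction rejects with the same probabilities as in the table while successful families are unchanged.

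**4. Success rates implied by Aim 1.** Placebo odds are the megestrol odds times the stated odds ratio.
- 90%, OR .21, N = 72: 9 × .21 = 1.89, so 65% on placebo and 78% overall, about 16 failures.
- 90%, OR .18, N = 60: 9 × .18 = 1.62, so 62% on placebo and 76% overall, about 14 failures.
- 75%, OR .25, N = 60: 3 × .25 = .75, so 43% on placebo and 59% overall, about 25 failures.

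**5. Detectable d as success rises** (N = 60, two-sided .05, 80% power): .75 at 36/24, .80 at 42/18, .87 at 46/14, 1.23 at 54/6. These are in units of the SD of the change. In visit SDs, the 76% figure is .87 × 1.18 = 1.03 at ρ = .3 and .87 × .63 = .55 at ρ = .8. With no failures the term does not exist.

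**6. The within-family contrast** (paired t, 80% power, ρ from .3 to .8): the detectable change is .44 to .23 SD over all 60 families, and .57 to .30 SD in 36 successes. It needs no failures.

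**The case against.** The strongest reply is that the plan documents its reading. Section 7.1 says that for 3A and 3B the grouping factor is success, and Hypothesis 1 defines the transition as reaching 90% of calories by mouth. On that reading a comparison with children who do not transition is deliberate, and it supplies a control that a before-after change lacks. This largely answers the point for 3B, where diverging slopes are predicted. What remains for 3B is that decline in unsuccessful families could produce the interaction without the week 24 gain over week 0. For 3A it does not answer the point: the hypothesis describes a rise and a return to baseline, and no within-family contrast is named.

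A reader might infer that the analysis is blind to a shared change. It is not: the trajectory modelled first would show one. It is simply not the designated test.

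A reader might also infer that Aim 1 assumes nearly all children succeed, so that the comparison group vanishes. The documents do not support this. The 90% applies to the megestrol arm, and no Aim 1 scenario exceeds 78% overall. The previous trial's 100% covers completers only, and section 1.3 describes the protocol's effectiveness as in combination with megestrol, which half of this trial will not receive. Section 3.3 also expects some weans to fail, and section 4.4.2 seeks outcomes after withdrawal. Against that, the primary population in section 7 is protocol-compliant. If Aim 3 uses it, the analysed children will resemble the completers who all succeeded, so few failures remains a real possibility.

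**Conclusion.** The point stands in this form. For 3A the designated test and the stated hypothesis have different nulls, and a rise common to all weaning families would be detected only at the 5% error rate. For 3B the mismatch is partial. The interaction loses sensitivity as success rises: detectable d goes from .75 at 60% to .87 at 76% and 1.23 at 90%. It fails altogether only if every analysed child succeeds.

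The zero-power result for a shared rise needs no assumption about correlation. The detectable effects assume alpha .05 two-sided and 80% power. The power figures also rest on an assumed 0.5-SD change and ρ between .3 and .8. At ρ = .8 the interaction is reasonably powered at 60% to 76% success if only one group changes. Aim 3 is secondary, so this is a change the plan should make and not a threat to the main result.

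**What to change.** In the same mixed model, before unblinding, prespecify within-family Estimate statements as the tests of 3A and 3B as worded:
- stress at week 14 versus week 0, and at week 24 versus week 0 (the return to baseline);
- quality of life at week 24 versus week 0;
- each in children who transition and in all families, with week 10 (before the wean) as a supporting reference visit.

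Keep the time-by-success interaction as the supporting comparison. Report it with each group's change and the number of unsuccessful children, and state that the within-family contrasts stand alone if failures are too few to fit it.

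Recalculate the section 7.1 detectable effects across about 60% to 78% success, with 90% as a sensitivity case, and state the alpha, power and within-family correlation used.

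The cost is plan wording and a few model statements on data already collected. The drawback is that a within-family change cannot separate the wean from the passage of time, and the successful subgroup is defined by a later outcome. That is why the all-families contrast is added and the interaction is kept.
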